8.6 Sample Size Calculation

Due to the exploratory nature of the study, the sample size was not determined based on formal statistical consideration, but rather on the feasibility of conducting the study as a whole. The study is intended to be analyzed descriptively. No formal hypothesis testing is planned.

There are six groups for active GBCA ingredients (Gadobutrol, Gadodiamide, Gadopentetic acid, Gadoteric acid, Gadoversetamide, and Gadoxetic acid). In each group, two categories of renal function (stable (normal) renal function ($eGFR > 60 \text{ ml/min/1.73 m}^2$) versus at least moderate impaired renal ($\leq 60 \text{ ml/min/1.73 m}^2$) and two subgroups of dosing of GBCA (single / multiple) are to be evaluated.

Per active GBCA ingredient the recruitment targets are defined as follows:

- 5 subjects for stable normal renal function ($eGFR > 60 \text{ ml/min/1.73 m}^2$) and single dose
- at least 3 subjects and up to 5 subjects for stable normal renal function and multiple doses
- 5 subjects for at least moderate impaired renal function ($eGFR \leq 60 \text{ ml/min/1.73 m}^2$) and single dose
- up to 5 subjects for at least moderate impaired renal function ($eGFR \leq 60 \text{ ml/min/1.73 m}^2$) and multiple doses. For Gadobutrol and Gadoteric acid, at least 3 subjects are required. For Gadodiamide, Gadopentetic acid, Gadoversetamide, and Gadoxetic acid, there is no requirement to reach a specific number of subjects to achieve study completion.

The total target number of subjects enrolled in these groups will be at least 84.

The number of subgroups in the GBCA-naïve population is two according to renal function category (i.e. at least moderate impairment, and stable normal renal function) and should follow the distribution of the GBCA population. At least five subjects with stable normal renal function ($eGFR > 60 \text{ ml/min/1.73 m}^2$) and at least 10 subjects with at least moderate impaired renal function ($eGFR \leq 60 \text{ ml/min/1.73 m}^2$) will

Sponsor Name: Navitas Life Sciences GmbH
 Statistical Analysis Plan (SAP)
 Version No.: Final 1

Short Title of Study: Long-Term Retention of Gadolinium in Bone
 Sponsor Study No.: ALS-Gd64/001
 Date: 31JUL2019
 NLS Study No.: 665

be enrolled. Therefore, the total target number of GBCA-naïve subjects enrolled will be at least 15. Consequently, a minimum of 99 subjects in total shall be included in the study.

8.7 Interim Analysis

At the request of the EMA, an interim analysis was to be carried out on all subjects enrolled in the single dose subgroups for Gadobutrol, Gadoteric acid, Gadodiamide, and Gadopentetic acid once at least three subjects had been recruited to the single-dose subgroups for the 4 agents as well as on all subjects of the control group (naïve subjects).

A total of 55 subjects were eligible for the IA. Due to the fact, that the laboratory data for these subjects had to be unblinded, these subjects have already been classified before IA evaluation with regard to PDs. Since one subject had no concentration data available, only 54 subjects were included in the SAF.

To determine the Gd concentration in bone (trabecular and cortical) and skin (expressed as $\mu\text{g Gd / g}$) the IA based on the SAF and Gd concentrations was descriptively evaluated by:

- Renal function status: stable normal renal function ($\text{eGFR} > 60 \text{ ml/min/1.73 m}^2$),
 at least moderate impaired renal function ($\leq 60 \text{ ml/min/1.73 m}^2$)
- GBCA: Each of the 4 GBCAs (Gadobutrol, Gadoteric acid, Gadodiamide, and Gadopentetic acid) and control

No statistical tests have been calculated.

All data used in the interim analysis have been listed. All listings including subject identifier, GBCA type, renal function, and have been sorted by GBCA type, renal function, and subject identifier. Study investigational sites and analytical laboratories have been blinded to the IA results.

Details on the IA evaluation have been described in the interim SAP and the Abbreviated Interim Analysis Report, Version Final 1.0, dated 20181108.

8.8 Subgroup Analysis

This study was performed as a multinational multicenter study. Due to the small sample size of each stratification group, results will not be further stratified by age or country or center and nor special subgroup analyses will be performed.

The subjects who have undergone two surgeries on study will be analyzed as a subgroup, at least for Gd concentration in bone and skin. Descriptive statistics will be calculated for the difference of Gd concentration in bone (trabecular and cortical) and in skin at the time of first and the time of second surgery. Since the number of subjects in this subgroup is so low, no stratification will be performed.

Sponsor Name: Navitas Life
Sciences GmbH

Statistical Analysis Plan (SAP)

Version No.: Final 1

Short Title of Study: Long-Term Retention of
Gadolinium in Bone

Sponsor Study No.: ALS-Gd64/001

Date: 31JUL2019

NLS Study No.: 665

8.9 Definitions and Derived Variables

Variable / Term	Definition / Way of calculation
Test group	Refers to subjects with GBCA exposure
Control	Includes GBCA naïve subjects
Stable normal renal function	Stable normal renal function (eGFR > 60 ml/min/1.73 m ²),
Impaired renal function	Impaired renal function (eGFR <=60 ml/min/1.73 m ²) The groups of sever and moderate impaired renal function are combined as explained in the section 10.
Single dose	Only one application of GBCA (0.1 mmol per kg body weight for Gadobutrol, Gadoteric acid, Gadodiamide, and Gadopentetic acid; 0.025 mmol per kg body weight for Gadoxetic acid)
Multiple dose	More than one application of GBCA or one injection with higher than approved standard dose (0.1 mmol per kg body weight for Gadobutrol, Gadoteric acid, Gadodiamide, and Gadopentetic acid; 0.025 mmol per kg body weight for Gadoxetic acid))
Time between most recent administration of GBCA [month] and surgery	= (Date of surgery – date of most recent GBCA administration +1 day) / 30.25
Time of cumulative GBCA doses [month]	= (Date of surgery – date of first GBCA administration +1 day) / 30.25
Cumulative dose of GBCA (mmol)	= Sum of all administrated GBCA doses
Cumulative dose of erythropoietin [IU/L]	= Sum of all administrated erythropoietin doses

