## 5.3 Selection of dose and timing for each patient

This protocol focuses on the exploration of long-term Gd-retention in patients exposed to GdCAs. There is no upper limit for the time-interval between GdCA administration and sample collection during the scheduled orthopaedic surgical procedure, based on prior evidence that Gd may be detectable in bone 8 years after injection of GdCA (21). In this protocol, the time interval between the last dose of GdCA and surgery must be at least 1 month. The enrolment of patients with a wide range of times between GdCA injection and time of tissue sample collection during surgery may support the evaluation of long-term Gd-retention.

The study will evaluate for the subgroups with a history of single GdCA dose administration only patients who received the approved standard dose for each of the GdCAs. For the products with the active ingredients Gadobutrol, Gadodiamide, Gadopentetic acid, Gadoteric acid, and Gadoversetamide this is 0.1 mmol per kg body weight. For Gadoxetic acid, a single dose is 0.025 mmol per kg body weight.

Patients in the respective multiple doses subgroups will have received either repeated doses or a single or multiple higher than the approved standard dose, and thus higher cumulative concentrations of the same GdCA. Any higher dose than 120% of the standard dose of GdCA will be analysed as part of the multiple doses subgroup. In both dose subgroups, the individual and total combined doses administered will be documented and evaluated.

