## 5.5 Blinding and randomisation

There will be no randomisation. The analysis of bone and skin tissue samples will be done in a blinded manner.

Patients will be registered centrally via an interactive web response system (IWRS). This system will be connected with the eCRF and will be accessible 24 hours/7 days a week. Each patient will be assigned to a stratified enrolment group defined by the GdCA ingredient administered (or control), renal function category (moderate impairment, severe impairment or stable normal renal function eGFR > 60 ml/min/1.73 m^2) and dosing number (single / multiple). Confirmation of patient enrolment will be provided to the enrolling centre and shall be retained by the investigator.

Once a stratification group is complete, no further enrolment into that group will be allowed. All participating centres will be notified upon the completion of each enrolment group.

The data of all patients on study will be de-identified by allocation of a patient number to each patient enrolled. No identifying information will be contained in the study eCRF. Patient numbers will be issued sequentially to each centre upon patient enrolment.

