#### 8.1.2 Primary and secondary analyses

##### Statistical methods:

Study data will be analysed descriptively. No formal hypothesis testing is planned.

All parameters will be analysed for the per protocol population using descriptive statistics including confidence intervals whenever appropriate. Details will be defined in a statistical analysis plan (SAP), which will be signed prior to unblinding of the samples.

Descriptive statistical methods will be used to summarise the results of the study. The following descriptive statistics will be calculated for continuously distributed data and for ordered categorical data (ordinal data) if applicable:

- N (number of non-missing measurements)
- Arithmetic mean
- Standard deviation
- Coefficient of variation (CV),
- Geometric mean

- Geometric standard deviation (re-transformed standard deviation of the logarithms)
- Corresponding CV
- Minimum
- Median
- Maximum

For ordered categorical data and nominal data, absolute and relative frequencies (in %) will be calculated.

Group or stratification variables due to the study design are:

- GdCA test group or control
- Renal function category (moderate impairment, severe impairment or stable normal renal function eGFR > 60 ml/min/1.73 m^2, Figure 3)
- Single (one injection of standard dose) or multiple (more than one injection or one injection with higher than standard) doses of GdCA administered

The elapsed time from dosing of GdCA until surgery will be classified and will also be used for stratification.

Statistical tables will compare all GdCA groups pooled as well as each GdCA group separately versus the control group. They will be further stratified according to renal function category (3 groups), single / multiple doses of all patients (2 groups), and the combination of “renal function with “single / multiple doses”.

The primary analysis encompasses the evaluation of Gd concentration in trabecular and cortical bone. The secondary analysis deals with Gd concentration in skin as well as the parameters specified below.

Descriptive analyses include

- Gd concentration in bone (trabecular and cortical) and skin will be expressed as nmol Gd / g bone or skin.
- Gd concentration in bone (trabecular and cortical) and skin as a function of time elapsed between GdCA injection and surgery. Additional stratification classifications of time after dosing of Gd will be specified in the SAP.

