7.3 Parameters

7.3.1 Evaluation Parameters

Primary Parameter

- Total Gd concentration in trabecular bone in $\mu\text{g/g}$
- Total Gd concentration in cortical bone in $\mu\text{g/g}$

Secondary Parameter

- Total Gd concentration in skin tissue in $\mu\text{g/g}$
- Gd concentration in bone (trabecular and cortical) and skin as a function of time elapsed between GBCA injection and surgery
- Number of single (one injection of standard dose) or multiple (more than one injection or one injection with higher than standard) doses
- Cumulative dose of GBCA i.e total mmol administered prior to surgery.
- Time elapsed between most recent administration of GBCA [month] and surgery.
- Time of cumulative GBCA doses [months]
- Time intervals of dosing
- eGFR [ml/min/1.73 m^2]
- Potential co-factors for NSF and susceptibility factors, based on the following data and in the limit of their availability in medical history of the patients:
 - eGFR;
 - cumulative dose of GBCA,
 - co-existing vascular, thrombotic and/or pro-inflammatory events
 - serum concentrations of calcium, phosphorus, sodium, iron, potassium and zinc
 - Any event which may have led to Iron mobilization, including concomitant iron drug
 - Cumulative dose of erythropoietin [IU/L]
 - T4 and TSH
- Concomitant drug treatments with potential impact on bone metabolism:
 - biphosphonates
 - estrogens
 - calcitonin
 - calcitriol
 - fluoride salts
 - vitamin D
 - corticosteroids
- Concentration of Ca, P, Na, Zn, K and Fe in skin and in tissue of both trabecular and cortical bone, determined by ICP-MS
- Clinical histological evidence of NSF (determined by an experienced dermatopathologist).
- Subjects who have undergone 2 surgeries

Sponsor Name: Navitas Life Sciences GmbH
 Statistical Analysis Plan (SAP)
 Version No.: Final 1

Date: 31JUL2019

Short Title of Study: Long-Term Retention of Gadolinium in Bone

Sponsor Study No.: ALS-Gd64/001
 NLS Study No.: 665

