8.2.1 Group and Stratification Variables

- GBCA test group or control
- Renal function category (at least moderate impairment (eGFR \leq 60 ml/min/1.73 m²), stable normal renal function (eGFR $>$ 60 ml/min/1.73 m²))
- Single (one injection of standard dose) or multiple (more than one injection or one injection with higher than standard) doses of GBCA administered
- Combination of “renal function with “single / multiple doses”
- Elapsed time from first dosing of GBCA until surgery (cumulative dose of GBCA) will be classified and will also be used for stratification.

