9 STATISTICAL ANALYSES

The statistical analysis will be carried out for all GBCA groups pooled as well as each GBCA group separately and the control group. They will be further stratified according to renal function category (2 groups), single / multiple doses (2 groups), and the combination of “renal function with “single / multiple doses”.

All tables will be programmed for the control group, all GBCA groups pooled as well as for each GBCA group separately. Each table will be presents by all stratification for the renal function categories (2 groups = 2 columns). Repeat tables will be produced by treatment/renal function and dose (single / multiple doses) combined.

Because standard point estimates may be biased when the total number of BLQ values is large (such as when it exceeds 1/3 of the total), the descriptive analysis should only to be calculated if at least 2/3 of the individual data had been measured and found to be above the LLOQ (rationale based on PhUSE_CSS_WhitePaper_PK_final_25March2014.pdf).

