9.6 Analysis

9.6.1 Primary Analysis

The primary evaluation parameters Gd concentration in bone (trabecular and cortical) will be descriptively tabulated for the control group and each of the 6 GBCAs (Gadobutrol, Gadodiamide, Gadopentetic acid, Gadoteric acid, Gadoversetamide, and Gadoxetic acid) and presented by renal function status: stable normal renal function (eGFR > 60 ml/min/1.73 m²) and at least moderate impaired renal function (<=60 ml/min/1.73 m²). For mean, SD and %CV the geometric equivalents will be calculated.

The primary analysis will be performed on the full analysis (FAS) and the per protocol set (PPS) (see definitions 8.3).

No statistical tests will be calculated.

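### The SAP defines multiple dose without the protocol's 120% cut, so read literally it moves one-injection patients above 100% and up to 120% of standard into the multiple-dose stratum

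*SAP*

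**What the plan says.** **Protocol 5.3** first describes multiple-dose patients in general terms: repeated doses, or dosing above the approved standard. The next sentence gives the rule: "Any higher dose than 120% of the standard dose of GdCA will be analysed as part of the multiple doses subgroup". The same section limits single-dose evaluation to patients who received the approved standard dose, 0.1 mmol/kg for five agents and 0.025 mmol/kg for Gadoxetic acid.

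**Protocol 8.1.2** lists the stratification variable without the cut: "multiple (more than one injection or one injection with higher than standard) doses of GdCA administered".

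**SAP 8.2.1** carries that wording over: "Single (one injection of standard dose) or multiple (more than one injection or one injection with higher than standard) doses of GBCA administered". SAP 7.3.1 does the same. In the definitions table of **SAP 8.9**, multiple dose is "More than one application of GBCA or one injection with higher than approved standard dose", followed by the mmol/kg values. The SAP nowhere mentions 120%.

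**SAP 10** says that the SAP prevails where it contradicts the protocol, and it tabulates the differences. The dose cut is not among them.

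**Use of the stratum.** SAP 9: "Repeat tables will be produced by treatment/renal function and dose (single / multiple doses) combined". By contrast, the bone gadolinium results in SAP 9.6.1 "will be descriptively tabulated for the control group and each of the 6 GBCAs", by renal function, with no split by dose.

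**The concern.** The protocol's only numerical rule for separating single from multiple dose is missing from the document that governs the analysis. SAP 8.9 is where a programmer would look, and it gives exact doses and no tolerance. Coded as written, an injection slightly over the nominal dose, for example from rounding of the injected volume, makes the patient multiple dose.

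The repeat tables by agent, renal function and dose are where a reader would look for an effect of cumulative exposure. A near-standard single exposure placed in the multiple-dose column makes that column harder to interpret. The reader would also not know which rule had been applied. Protocol 5.5 adds a third possibility: the web response system assigned patients to a single or multiple group at enrolment, and the SAP does not say whether the tables use that group or the 8.9 definition.

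**Working it through.** **1. The plan's own totals.** From Table 1 (protocol section 3, SAP 8.2.2), the minimum cell targets are 5 + 3 + 5 + 3 = 16 for each of Gadobutrol and Gadoteric acid, and 5 + 0 + 5 + 3 = 13 for each of the other four agents.

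- Test group: 2 × 16 + 4 × 13 = 32 + 52 = 84.
- With 15 controls: 84 + 15 = 99.

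Both stated totals reproduce, and neither depends on which dose cut is used.

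**2. Where the two rules differ.** For one injection, protocol 5.3 gives multiple if the dose exceeds 120% of standard. SAP 8.9 read literally gives multiple if it exceeds 100%.

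| One injection, % of standard | Dose, five agents (mmol/kg) | Dose, Gadoxetic acid (mmol/kg) | Protocol 5.3 | SAP 8.9, literal |
|---|---|---|---|---|
| 95 | 0.095 | 0.02375 | single | single |
| 100 | 0.100 | 0.025 | single | single |
| 105 | 0.105 | 0.02625 | single | multiple |
| 110 | 0.110 | 0.0275 | single | multiple |
| 120 | 0.120 | 0.030 | single | multiple |
| 150 | 0.150 | 0.0375 | multiple | multiple |

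The upper limits are 1.2 × 0.1 = 0.12 and 1.2 × 0.025 = 0.030 mmol/kg. For an assumed 70 kg patient, the band runs from above 7.0 to 8.4 mmol, or from above 1.75 to 2.10 mmol for Gadoxetic acid.

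**3. Effect of one moved patient on a cell.** Targets are 5 for single dose. For multiple dose they are 3 to 5, except 0 to 5 in the impaired-renal-function cells of four agents.

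- Single-dose cell: 5 becomes 4, a loss of 1/5 = 20%.
- Multiple-dose cell of 3 becomes 4; the moved patient is 1/4 = 25% of it.
- Multiple-dose cell of 5 becomes 6; the moved patient is 1/6 = 17% of it.
- Multiple-dose cell of 0 becomes 1; the moved patient is the whole cell.

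**4. Effect on whether a cell is summarised.** SAP 9 gives descriptive statistics only if at least 2/3 of values are above the LLOQ. Suppose every value in a multiple-dose cell is above it and every moved patient is below. One moved into a cell of 3 gives 3/4 = 75%, still summarised; two give 3/5 = 60%, not summarised. Into a cell of 5, the figures are 5/6 = 83% and 5/7 = 71%, both still summarised. In this illustration only the two-into-three case changes the output.

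**5. What cannot be computed.** Neither document gives the number of one-injection patients above 100% and up to 120%.

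**The case against.** The best defence is that nothing was changed. Protocol 5.3 itself uses almost the same general phrase as SAP 8.9 and then makes it operational at 120%. The SAP and protocol 8.1.2 may simply use the phrase as shorthand, with 5.3 still supplying the rule. SAP 10 says that the analysis follows the protocol as well as the SAP, and a general phrase need not contradict a specific cut. This is a fair reading, and it means that the missing entry in SAP 10 is not evidence of an undisclosed change. A reader might infer that the tolerance was deliberately dropped; the documents do not show that. The ambiguity remains, because 8.9 is the definitions table, gives exact doses and does not point to 5.3.

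Second, protocol 5.3 does not state that doses up to 120% are single; it only implies it, and it also restricts single-dose evaluation to the standard dose. That is correct. But a 120% cut has little purpose if 101% is already multiple.

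Third, if the tables use the enrolment group, the wording of 8.9 moves nobody. That is possible, but the SAP does not say so.

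Fourth, dose and dosing dates are to be listed by patient (SAP 16, listings 16.2.6.1 and 16.2.6.2), so a reader might be able to find patients in the band. The rule applied would still have to be guessed.

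**Conclusion.** The point holds as a gap in a definition. Taken literally, the SAP's rule differs from the implied rule of protocol 5.3 for one injection above 100% and up to 120% of standard. The two agree for every other dose. The consequence is limited to the repeat tables by dose, where one patient is a material share of a cell.

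A reader might go further and infer that patients have been misclassified, or that the primary bone results or a dose-effect estimate are biased. The documents do not support this. The count in the band is unknown and may be zero, the SAP 9.6.1 tables by agent and renal function are the same under either rule, and no test or formal comparison of multiple with single dose is planned.

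The conclusion rests on two assumptions: that 8.9 is applied as written, and that 5.3 is meant to keep doses up to 120% in the single-dose group. The correction is worth making because it is cheap and removes doubt about a stratum used throughout the tables.

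**What to change.** In SAP 8.9, define:

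- **Multiple dose:** more than one injection, or one injection above 120% of the approved standard dose (above 0.12 mmol/kg, or above 0.030 mmol/kg for Gadoxetic acid).
- **Single dose:** one injection of the standard dose, with doses up to 120% counted as standard. Underdosed patients stay subject to the existing eligibility and protocol deviation review, so the rule does not admit them by default.

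Have 8.2.1 and 7.3.1 refer to 8.9 rather than restate the definition. Add Gadoversetamide to the dose rows of 8.9, which omit it; protocol 5.3 gives 0.1 mmol/kg. State that the analysis stratum is derived from recorded dose and weight by this rule, and report any patient whose derived stratum differs from the enrolment group. If a cut at 100% is really intended, list it with its reason in SAP 10.

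The cost is one definition, two cross-references and one short count. Protocol 7.2.1 already collects the dose and a body weight from within 4 weeks before the injection, so no new data are needed and the 84 and 99 targets stand.

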### Patients having received GdCA

7. Patient belongs to one of the following subgroups with respect to the number of GdCA doses received and the status of their renal function:
  - a) patient (total to enrol = 5) has **stable impaired renal function** (at least moderate impairment, eGFR  $\leq$  60 ml/min/1.73 m^2) and has received **one GdCA injection** at the standard dose (0.025 mmol per kg body weight for Gadoxetic acid and 0.1 mmol per kg body weight for all other agents)

or

b) Up to 5 patients with **stable impaired renal function** (at least moderate impairment, eGFR  $\leq$  60 ml/min/1.73 m $^2$ ) and has received **more than one injection** of the same GdCA.

- Gadodiamide, Gadopentetic acid, Gadoversetamide, and Gadoxetic acid groups: no target number. Patients should be recruited to this subgroup throughout the study duration, but there is no requirement to reach a specific number of patients in this subgroup to achieve study completion.
- Gadobutrol and Gadoteric acid groups: at least 3 patients. If the target of 3 patients is reached, but the study has not yet completed, then recruitment to this group should be continued during the remaining study time.

or

c) patient (total to enrol = 5) has **stable normal renal function** (eGFR  $>$  60 ml/min/1.73 m $^2$ ) and has received **one GdCA injection** at the standard dose (0.025 mmol per kg body weight for Gadoxetic acid and 0.1 mmol per kg body weight for all other agents)

or

d) patient (total to enrol = 3 to 5) with **stable normal renal function** (eGFR  $>$  60 ml/min/1.73 m $^2$ ) who have received **more than one injection** of the same GdCA. If the target of 3 patients is reached, but the study has not yet been completed, then recruitment to this subgroup should be continued during the remaining study time, stopping when 5 patients have been recruited to this subgroup, or when all other subgroups have reached their minimum target for recruitment, whichever comes first.

8. A minimum of 1 month have elapsed between GdCA dose and the scheduled orthopaedic surgical procedure.

9. Patient GdCA history, including dose(s), date(s), and product(s) administered is complete and accurate.

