8.5 Data Handling

There will be no imputation of missing data. All data will be analyzed as they appear in the data base.

Since the geometric mean (the retransformed mean of the logarithmized values) and CV% cannot be calculated in the presence of zero values, the values BLQ were implemented in the IA analysis by half the LLOQ (i.e. 0.025) instead of zero for the calculation of the descriptive statistics. This approach will also be

Sponsor Name: Navitas Life
 Sciences GmbH
 Statistical Analysis Plan (SAP)
 Version No.: Final 1

Short Title of Study: Long-Term Retention of
 Gadolinium in Bone
 Sponsor Study No.: ALS-Gd64/001
 Date: 31JUL2019
 NLS Study No.: 665

used for the final analysis. Therefore, values below the limit of quantification (LLOQ) will be replaced by half of the LLOQ (i.e 0.025) instead of zero for the calculation of the descriptive statistics. For adverse events the following rules will be applied:

- AEs with unknown onset date/time will be counted as treatment emergent AEs.
- AEs with unknown end date/time will be counted as an ongoing AE.
- AEs with unknown relationship to GBCA will be counted as related in AE summary tables.
- If for the calculation of a time period the full date format ddmmmyyyy is needed, missing entries will be imputed as follows:
 - Missing day in start date of a time period is imputed by the first day of the month;
 - Missing day in stop date of a time period is imputed by the last day of the month;
 - Missing month in start date of a time period is imputed by January of the year;
 - Missing month in stop date of a time period is imputed by December of the year;
 - Missing year is not imputed.

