9.6.2 Secondary Analysis

The secondary evaluation parameter Gd concentration in skin (expressed as µg Gd /g) will be analyzed for the FAS analogously to the primary parameter.

For the following secondary parameter number and percentages or arithmetic summery statistics will be presented for the FAS where applicable.

- Time elapsed between most recent administration of GBCA and surgery in month
- Time of cumulative GBCA doses [month]
- Potential co-factors for NSF and susceptibility factors, based on the following data and in the limit of their availability in medical history of the subjects:
 - eGFR
 - cumulative dose of GBCA
 - co-existing vascular, thrombotic and/or pro-inflammatory events
 - serum concentrations of calcium, phosphorus, sodium, iron, potassium and zinc

Sponsor Name: Navitas Life
 Sciences GmbH
 Statistical Analysis Plan (SAP)
 Version No.: Final 1

Short Title of Study: Long-Term Retention of
 Gadolinium in Bone
 Sponsor Study No.: ALS-Gd64/001
 Date: 31JUL2019
 NLS Study No.: 665

- any event which may have led to iron mobilization, including concomitant iron drug
- cumulative dose of erythropoietin
- T4 and TSH.
- Concomitant drug treatments with potential impact on bone metabolism: biphosphonates, estrogens, calcitonin, calcitriol, fluoride salts, vitamin D, corticosteroids.
- Concentration of Ca, P, Na, Zn, K and Fe in skin and in tissue of both trabecular and cortical bone determined by ICP-MS.

No statistical tests will be calculated.

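### SAP 8.9 converts days to months with a 30.25-day month (a 363-day year) plus one day, overstating both defined elapsed times slightly against a mean calendar month

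*SAP*

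**What the plan says.** SAP 8.9 (Definitions and Derived Variables) defines two elapsed times in months. Each starts from the date of surgery.

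- **Most recent dose to surgery:** the formula subtracts the "date of most recent GBCA administration +1 day) / 30.25".
- **First dose to surgery** (labelled time of cumulative doses): the formula subtracts the "date of first GBCA administration +1 day) / 30.25".

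Neither document explains 30.25 or the added day, and neither defines a month in any other way.

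The two times are used as follows:

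- SAP 9.6.2 summarises both; the first is listed as "Time elapsed between most recent administration of GBCA and surgery in month". The SAP's table list gives time since last administration its own table, 14.6.2.2.
- SAP 8.2.1 says that time from first dosing "will be classified and will also be used for stratification". It gives no class limits.
- Protocol 5.3 sets the range: "In this protocol, the time interval between the last dose of GdCA and surgery must be at least 1 month", and "There is no upper limit for the time-interval between GdCA administration and sample collection".

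SAP 10 states that the SAP prevails where it contradicts the protocol.

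**The concern.** The study asks about long-term retention, so time since dosing is its main descriptive axis besides agent, renal function and dose. A unit labelled month should be a month. The divisor 30.25 corresponds to no calendar year and looks like a slip.

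The added day is a counting convention. It suits a duration in which both end days count, but fits less well with time between two events. The study's own schedule (Protocol 7.1, SAP 7.2) calls surgery day 0, whereas under this formula an interval of zero days would read as 0.03 month.

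Both features push the value up, so they add rather than cancel. At stake are the reported means, medians, minima and maxima of elapsed time and, if time classes are later set, the class of patients just below a limit.

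**Working it through.** **Inputs.** The divisor of 30.25 days and the added day come from SAP 8.9. The comparison month, 365.25/12 = 30.4375 days, is an assumption of this check, because the documents give none. The 8-year example is the interval that Protocol 5.3 cites for detectable gadolinium in bone.

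**Step 1: can 30.25 be reproduced?** 12 × 30.25 = 363 days. The candidate years give:

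- 365.25/12 = 30.4375
- 365.2425/12 = 30.4369
- 365/12 = 30.4167
- 366/12 = 30.50
- 364/12 = 30.33
- 360/12 = 30.00

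None gives 30.25.

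**Step 2: separate the two parts.** For an interval of d days, the SAP value is (d + 1)/30.25 = d/30.25 + 1/30.25.

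- Divisor: 30.4375/30.25 = 1.0062, so +0.62%. Against 365/12 it is +0.55%, and against 366/12 it is +0.83%.
- Added day: 1/30.25 = 0.033 month, whatever the length of the interval.

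Hence SAP value = 1.0062 × (d/30.4375) + 0.033.

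**Step 3: put numbers in.**

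| Interval | d (days) | SAP: (d + 1)/30.25 | d/30.4375 | Excess (months) | Excess (days) |
|---|---|---|---|---|---|
| 1 year | 365.25 | 12.107 | 12.000 | 0.107 | 3.3 |
| 2 years | 730.5 | 24.182 | 24.000 | 0.182 | 5.5 |
| 5 years | 1826.25 | 60.405 | 60.000 | 0.405 | 12.3 |
| 8 years | 2922 | 96.628 | 96.000 | 0.628 | 19.1 |
| 10 years | 3652.5 | 120.777 | 120.000 | 0.777 | 23.6 |

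The SAP value exceeded the mean-month value for every whole-day interval from 0 to 9,999 days, and also with 365/12 or 366/12 as the month.

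**Step 4: effect on the summaries.** The relation in step 2 is linear and increasing. Mean, median, minimum and maximum are therefore each multiplied by 1.0062 and raised by 0.033 month, and the SD is multiplied by 1.0062. The order of patients by time does not change. If values are rounded to one decimal (an assumption about display), every whole-day interval from 366 to 3,652 days shows a different figure, as do 73.5% of those from 30 to 365 days.

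**Step 5: effect on time classes, if there were any.** Suppose a class began at 12, 60 or 96 months. These cuts are assumptions; the SAP has none. First-dose intervals of 362–365, 1,814–1,826 or 2,903–2,921 days would then enter the higher class under the SAP formula but not under d/30.4375. For example, (362 + 1)/30.25 = 12.00, whereas 365/30.4375 = 11.99.

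**The case against.** The strongest reply is that nothing of substance depends on this. The analysis is descriptive and without tests (SAP 8), the primary variables are concentrations, the same formula applies to every exposed patient, and dosing timepoints are listed (listing 16.2.6.2). All of that stands, and it sets the size of the point. It does not make 30.25 a correct divisor.

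Three stronger readings are tempting, and the documents do not support them.

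- **That the formula lets patients past the 1-month minimum.** The rule "A minimum of 1 month have elapsed between GdCA dose and the scheduled orthopaedic surgical procedure" is an eligibility criterion, checked by the investigator from recorded dates at screening (Protocol 7.2.1). The SAP is dated 31 July 2019 and recruitment ended in December 2018 (SAP 7.1), so its formula could not have affected enrolment. The per-protocol set rests on the criteria and a data review (SAP 8.3, 8.4), not on this derived variable. Nor does a 30-day interval show a wrong crossing. It reads 31/30.25 = 1.02 by the SAP and 30/30.4375 = 0.99 by the mean month, yet 15 April to 15 May is one calendar month of 30 days, and the documents do not define a month.
- **That every elapsed time is too long.** This holds only against a mean month. Against whole calendar months, a 28-day February span reads 29/30.25 = 0.96. The finding also covers only the two defined times; time intervals of dosing (SAP 7.3.1) have no formula.
- **That patients will be put in the wrong stratum.** Only first-dose time is to be classified, no limits are given, SAP 9 stratifies its tables by renal function and dose, and no listed table title shows gadolinium by time class. A shift is possible only if limits are set. The missing limits are a separate matter.

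The added day is also fairly defended as a uniform convention that no rule in the documents forbids. It is better called ill-suited to time between two events than called an error.

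**Conclusion.** The divisor is wrong as written, and nothing in either document justifies or corrects it. Against a mean calendar month of 30.4375 days, both times defined in SAP 8.9 are overstated by 0.62% plus 0.033 month: about 0.11 month at 1 year, 0.40 at 5 years and 0.63 at 8 years. The total excess is below 1% from one year on.

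The consequence is confined to the reported elapsed-time summaries and, conditionally, to any later classification of first-dose time. The size rests on the mean month as reference; with 365/12 or 366/12 the divisor effect is 0.55% or 0.83%, and its direction is the same. Partial dates are left out: SAP 8.5 provides that "Missing day in start date of a time period is imputed by the first day of the month", which could lengthen an interval further, although inclusion criterion 9 asks for a complete dosing history.

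**What to change.** In both lines of SAP 8.9, use (date of surgery − date of administration) / 30.4375, and state that 30.4375 = 365.25/12. If the added day is kept as a house convention, say that the interval counts both end dates. If limits for first-dose time are set later, apply them to the corrected variable.

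The cost is one expression in two SAP lines and in the derivation program. No data collection, sample size or concentration result changes, and the SAP lists no interim table corresponding to 14.6.2.2 that would need to be reconciled. If the database is already locked, a corrected derivation and a sentence in the study report are enough.
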